7.3 End of study visit

The final visit will be a clinic visit, scheduled at 12 months (\pm 1 week) after randomization; the following assessments will be performed:

1. Evaluation of possible relapses, compliance with treatment schedule and adverse events;
2. Recording of clinical parameters: weight, arterial blood pressure, heart rate;
3. Neurological examination;
4. General clinical history: concomitant diseases and medications;
5. Assessment of birth control methods for women in childbearing age
6. Recording of the plasma concentration of the assigned drug (only if required as per clinical practice);
7. Report of a standard, interictal EEG if performed as per clinical practice;
8. Administration of the QOLIE-31 and PSQ-18 inventories;
9. Receipt of the seizure diary and control for quality and completeness.

The patient will exit the study and antiepileptic treatment will be continued or modified in case of seizure relapse or changed due to adverse events, if required by the local investigator.

7.4 Treatments Medication Compliance

Subjects will be instructed to use the study medication in compliance with the treatment schedule. If

the subject is compliant with the schedule and no seizures are reported, he/she will be advised to come to the Centre for the next visit or to be contacted by phone; otherwise, he/she will exit the study and the final visit will be performed within 72 hours. The treating physician will be responsible for the assessment of subject's compliance with study medication at each visit. Compliance will be measured counting the weekly amount of assigned drug. Poor compliance will be defined by taking less than 75% of assigned dose and/or absence of drug intake for 2+ consecutive days. This information will be recorded and retained in the subject's record.

Subjects will be instructed to return all drug consumed (empty) and unused, as well as a completed diary, at the end of study visit and during each visit at discretion of the physician before end of study visit. Reconciliation of drug consumed and drug remaining will be logged on the drug dispensing and return log, signed and dated. Any discrepancies noted will be investigated, resolved, and documented prior to destruction of unused study drug. The investigator will be responsible for the assessment of subject compliance with study medication at each visit and the count of returned study medication. This information will be recorded and retained in the subject's record.

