2.3 Primary endpoint

The primary end-point is a treatment failure motivated by the need to change the assigned dose or the assigned drug for seizure relapse.

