6.4 Treatment blinding

The study is single-blind. Only the evaluating physician will be blinded to the assigned treatment schedule.

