6.5 Brand & generic drugs

For each product, the treating physician can use the brand or the generic formulation. However, physicians and patients will be allowed to shift from brand to a generic formulation (where available) and vice versa and from one generic formulation to another during the study period.

6.6 Need to change the study drug or add another compound and premature withdrawal

An unscheduled phone contact will also take place soon after a relapse: the patients will also be instructed to call a member of the study staff within 24 h after an ictal event. If the study staff is confident about the epileptic nature of the event, the treating physician may decide to modify the treatment schedule; the patient will be thus instructed to change the AED doses or the treatment and come for the final visit within 72 hours. Otherwise, the patient will be invited to come for a clinic visit within the next 72 hours.

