Follow-up visits will be scheduled at the discretion of the caring physician but telephone contacts will be programmed at 4 weeks, 3, 6, 9 and an on-site clinic visit at 12 months. An interval of ± 1 week for the visit schedule is permitted. During each contact the patient will be asked to report any seizure recurrence, adverse event and any additional information deemed important for the management of the disease. Patients will be invited to read the diaries and verify if any missing or incomplete information was present.

The following evaluations will be performed during site visits:

1. Evaluation of possible relapses, compliance with treatment schedule and adverse events;
2. Recording of clinical parameters: weight, arterial blood pressure, heart rate;
3. Neurological examination;
4. General clinical history: concomitant diseases and medications;
5. Recording of the plasma concentration of the assigned drug and laboratory examinations previously specified (only if required as per clinical practice);
6. Administration of the QOLIE-31 and PSQ-18 inventories (only at 12 months);
7. Report of a standard, interictal EEG if performed as per clinical practice;
8. Report of the daily intake of assigned drug and timing of the assigned dose;
9. Report of all the contacts with the National Health System (NHS) for the management of seizures and AEDs;
10. Receipt of the seizure diary, control for quality and completeness, and delivery of a new diary.

The diaries will be examined by an investigator different from the treating physician (the evaluating physician) who will be blinded to the assigned drug schedule

The following evaluations will be performed during phone contacts:

1. Evaluation of possible relapses, compliance with treatment schedule and adverse events;
2. General clinical history: concomitant diseases and medications;
3. Report of the daily intake and timing of the assigned dose;
4. Report of a standard, interictal EEG, if performed;
5. Recording of the plasma concentration of the assigned drug and laboratory examinations previously specified, if performed;
6. Report of all the contacts with the NHS for the management of seizures and AEDs.

In case of seizure relapse or treatment change due to adverse events, the patient will exit the study and antiepileptic treatment will be modified if required by the treating physician.

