treatment regimens. Numerical variables will be described using means, standard deviations, medians and ranges, while categorical variables using frequencies and percentages. The proportion of patients experiencing the primary end-point over the entire follow-up will be estimated using Kaplan-Meier survival curves. The difference between the two treatment arms in the proportion of patients experiencing the primary endpoint, with 95% confidence intervals (95% CI), will be calculated at 1, 3, 6, 9 and 12 months, and compared to the non-inferiority margin (m). In presence of variables at admission having a different distribution in the two treatment groups and that could have an effect on treatment response (possible confounders), a multivariable analysis will be also performed using a Cox's proportional hazards model, adjusted for these variables. A hazard ratio (HR), with the corresponding 95% CI, will be reported, and compared to a relative risk (RR) obtained considering as reference the proportion of patients experiencing the primary endpoint in the standard dose arm (p_0) and taking into account the non-inferiority margin ($RR=(p_0+m)/p_0$). The secondary end-point will be evaluated using Kaplan-Meier survival curves, comparing the two treatment arms with the log-rank test. In presence of possible confounders with a different distribution in the two treatment arms at baseline, a Cox's proportional hazards model will be used. The QOLIE-31 total score, the seven PSQ-18 subscales scores at the last visit, and mean daily patient's costs will be compared, separately, between treatment arms using the t-test, the Wilcoxon-Mann-Whitney test, or a multivariable linear regression model. Subgroup analyses will be performed separately for sex, age groups, drug, seizure types (focal/focal-to-bilateral), etiology (known/unknown), and center.

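### Sections 6.6, 7.2 and 7.4 give different study-exit triggers for a reported event that staff doubt is epileptic, and section 10.4 does not say how such exits enter the primary analysis

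*Combined protocol and SAP*

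**What the plan says.** Three sections deal with what happens after a patient reports a possible seizure.

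- **Section 6.6** includes a judgement step: "If the study staff is confident about the epileptic nature of the event, the treating physician may decide to modify the treatment schedule", and the final visit follows within 72 hours. For an event about which staff are not confident, it says: "Otherwise, the patient will be invited to come for a clinic visit within the next 72 hours". That visit is not called final, and no exit is mentioned.
- **Section 7.4** lets the patient carry on if "the subject is compliant with the schedule and no seizures are reported"; "otherwise, he/she will exit the study and the final visit will be performed within 72 hours". It has no judgement step and no cross-reference to 6.6.
- **Section 7.2** uses a third wording: "In case of seizure relapse or treatment change due to adverse events, the patient will exit the study".

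Section 2.3 defines the primary endpoint as a "treatment failure motivated by the need to change the assigned dose or the assigned drug for seizure relapse". Section 10.4 states: "The proportion of patients experiencing the primary end-point over the entire follow-up will be estimated using Kaplan-Meier survival curves". It gives no censoring or counting rule for a patient who leaves without a primary event. On blinding, section 6.4 says: "Only the evaluating physician will be blinded to the assigned treatment schedule".

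**The concern.** For one and the same patient, with a reported event of doubtful nature, 6.6 gives a clinic visit and 7.4 gives study exit. Sites may follow either. Where 7.4 is followed, the patient leaves with no change of dose or drug for relapse. No primary event is recorded, and any later relapse goes unseen.

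If the analyst censors at exit, Kaplan-Meier treats the patient as if later relapse would occur at the average rate of those still followed. That is doubtful for someone who has just reported a possible seizure. If the later rate is higher, failure in that arm is understated. Those who report events and those who treat them know the dose, so such exits could be more frequent in one arm. The difference that is compared with the non-inferiority margin would then shift.

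**Working it through.** **1. The plan's own figure.** Section 10.6 assumes 60% seizure-free in both arms, one-sided 0.025 and 80% power. With a 15-point margin, n = (1.960 + 0.842)² × (0.24 + 0.24) / 0.15² = 167.4, so 168 per group. Total: 336 / 0.9 = 373.3, so 374. Both figures reproduce.

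**2. The passages side by side, for an event reported as a seizure but not judged epileptic.**

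| Section | What decides | Consequence |
|---|---|---|
| 6.6 | Staff confidence that the event is epileptic | Clinic visit within 72 hours; no exit stated |
| 7.2 | Seizure relapse | No exit, unless the event is taken as a relapse |
| 7.4 | Any seizure reported | Exit and final visit within 72 hours |
| 2.3 | Need to change dose or drug for relapse | No primary event |
| 10.4 | Kaplan-Meier | Handling of the exit not stated |

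**3. Size if such exits are censored.** The documents give no rate of unconfirmed events, so these inputs are assumptions: a share q of the arm exits this way (5-10% low dose, 2-5% standard dose), at times spread evenly over the 12 months, with a later relapse hazard k = 1.5 to 3 times average. The average hazard follows from 40% failure at 12 months: h = −ln 0.6 = 0.511.

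The mean chance of relapse in the time left after exit is I(k) = 1 − (1 − e^(−kh)) / (kh). This gives I(1) = 0.217, I(1.5) = 0.301 and I(3) = 0.488.

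Understatement in one arm = q × [I(k) − I(1)], where the bracket is 0.0845 for k = 1.5 and 0.2715 for k = 3.

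- Low-dose arm, smallest: 5% × 0.0845 = 0.42 points.
- Low-dose arm, largest: 10% × 0.2715 = 2.71 points.

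Shift in the between-arm difference = (q low − q standard) × [I(k) − I(1)]:

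| Exits, low v standard | k = 1 | k = 1.5 | k = 3 |
|---|---|---|---|
| 5% v 5% | 0 | 0 | 0 |
| 5% v 2% | 0 | 0.25 | 0.81 |
| 10% v 5% | 0 | 0.42 | 1.36 |
| 10% v 2% | 0 | 0.68 | 2.17 |

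The range over the assumed inputs is 0 to about 2.2 points. If the standard arm lost more patients, the sign would reverse.

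**4. Scale.** The standard error of the difference is √(2 × 0.40 × 0.60 / 168) = 5.3 points, so even the largest shift is under half of it. Suppose the true difference equals 15 points (55% v 40% failure). A 2.17-point understatement then raises the chance of wrongly declaring non-inferiority from 2.5% to about 6.0% (unpooled normal approximation, 168 per group).

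**5. Effect of the missing rule.** Counting an exit as a failure instead of censoring it raises that arm's estimate by about q × [1 − I(1)] = 0.783q, whatever k is. With 10% v 2%, the two choices differ by 8% × 0.783 = 6.3 points in the between-arm difference; with equal exits they do not differ.

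**The case against.** The best defence is that 7.4 concerns compliance and mentions seizures only in passing. Section 6.6 is the specific relapse procedure, and 7.2 lists an evaluation of possible relapses at every contact. An event that staff do not accept as epileptic is arguably not a seizure for 7.4 either. Both sections bring the patient in within 72 hours, when the event can be judged. Harm needs a site that doubts the event and still ends participation without changing treatment. This makes the problem less likely but does not remove it: 7.4 turns on what is reported, and nothing in it limits that to confirmed seizures.

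A second defence is that censoring is only one possible handling. Section 10.4 lists similar rates of seizure recurrence as the expected result, and 10.6 is sized on patients without a seizure, so an analyst might count these exits as failures. Over-reporting on low dose would then work against non-inferiority. This stands, and it is why no direction can be claimed.

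Third, the evaluating physician, who is blinded to the schedule, examines the diaries (7.2) and verifies them at each telephone contact (3.5). This partly protects the assessment of what was reported. It does not make the patient's reporting blind, and 7.4 does not make exit depend on that physician's view.

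Finally, the doubtful event is a narrow case. Under 7.2 even an accepted relapse leads to exit with treatment modified only where required, so a confirmed relapse may also leave without a primary event. That is true and is one more reason to align the sections.

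**Conclusion.** The inconsistency is in the current text and should be resolved: three sections give different exit triggers for the same event, one of them allows follow-up to end without a primary event, and the analysis section does not say what happens next.

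The statistical effect is conditional. It requires sites to apply 7.4 literally, the exits to be censored, later relapse to exceed the average, and the loss to differ between arms. Under the assumed inputs the shift is 0 to about 2.2 points. If later risk is average, the cost is lost follow-up and not bias.

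A reader might infer more, and the documents do not support it:

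- *That the trial is tilted toward non-inferiority.* Nothing shows which arm would report more doubtful events.
- *That these patients are censored.* No rule is stated.
- *That some shift is certain.* The assumed ranges include equal exits (5% in each arm), for which the shift is zero.

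**What to change.** Reconcile 6.6, 7.2 and 7.4 into one study-exit trigger, worded identically wherever it appears. Which clinical rule to adopt is for the sponsor, and treatment decisions stay with the treating physician. Whatever trigger is chosen:

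- go on collecting outcome data on patients with unconfirmed events through the scheduled telephone contacts and the 12-month visit, and count any later relapse that meets the primary endpoint;
- record in the e-CRF whether each reported event was judged epileptic;
- state in 10.4 how an exit after an unconfirmed event is handled in the Kaplan-Meier analysis, and add a sensitivity analysis that counts such exits as failures;
- tabulate unconfirmed events and the exits that follow them by arm.

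The cost is a short protocol amendment, which under section 11.4 needs local ethics approval at each participating institution, and one e-CRF item. The contacts are already scheduled, so no new visits are needed.

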7.5 Physical examination, weight, height

The patient will undergo a complete physical examination, including the measurement of height and weight.

7.6 Vital signs

Vital signs (systolic and diastolic blood pressure and heart rate) will be measured at each site visit by the treating physician or a designated person.

7.7 Scales and e-CRF

The QOLIE-31 inventory will be used at the baseline and last visit to measure HRQOL (Annex QOLIE-31). The Patient Satisfaction Questionnaire will be used at the baseline and last visit to measure patient's satisfaction (Annex PSQ-18).

The e-CRF used for the collection of demographic and clinical data is appended (Annex Case Report Form).

7.8 Subject Diary

Each subject will receive a diary in which he/she must record all seizure relapses (Annex Patient's diary). Any adverse events (AEs) occurring between one visit and the next, any new concomitant therapy, and any change in previously started study or concomitant therapies will be captured in the

diary.

7.9 Birth control method

All females of childbearing potential will declare, at randomization visit, to use highly effective birth control methods according to the recommendations related to contraception and pregnancy testing in clinical trials (1. combined (estrogen and progesterone) hormonal contraception associated with inhibition of ovulation (oral, intravaginal, transdermal); 2. progesterone-only hormonal contraception associated with inhibition of ovulation (oral, injectable, implantable); 3. intrauterine device (IUD); 4. intrauterine hormone-releasing system (IUS); 5. bilateral tubal occlusion; 6. vasectomised partner; 7. sexual abstinence). All females of childbearing potential will perform a pregnancy test at randomization visit and at the end of study visit.

During the following visits, a confirmation of birth control method will be asked. Patients who become pregnant during the study will be withdrawn.

In post-menopause women, a postmenopausal state is defined as absence of menses for 12 months without an alternative medical cause.

8. Safety

Safety monitoring for all patients enrolled in the study will be performed as done in clinical practice. Monitoring includes safety assessments and clinical evaluation, as scheduled in the flow chart. All AEs and serious adverse events (SAEs) will be recorded. Patient's diaries about AEs and/or concomitant medication will not be copied but will be considered source documents. AE documentation by the investigator will include the date of onset and duration, as well as the severity and causality of each AE, and the actions taken, including the discontinuation of the experimental drug, where required.

8.1 Adverse events

The Investigator is responsible for recording all AEs observed during the study.

Definition of AE: An AE is any untoward medical occurrence in a subject or clinical investigation subject administered a pharmaceutical product and which does not necessarily have a causal relationship with this treatment.

An adverse event can therefore be any unfavorable and unintended sign (including an abnormal laboratory finding, for example), symptom or disease temporally associated with the use of a medicinal product, whether or not considered related to the medicinal product.

Definition of SAE: A SAE is any untoward medical occurrence or effect that at any dose:

- Results in death
- Is life-threatening
- Requires inpatient hospitalization or prolongation of existing hospitalization
- Results in persistent or significant disability/incapacity
- Is a congenital abnormality/birth defect
- Medically significant events, which do not meet any of the criteria above, but may jeopardize the subject or may require medical or surgical intervention to prevent one of the other serious outcomes listed in the definition above.

Medical and scientific judgment should be exercised in deciding whether an event is “serious” in accordance with these criteria.

Hospital admissions and/or surgical operations planned before the study are not considered AEs if the illness or disease existed before the subject was enrolled in the study, provided that it did not deteriorate in an unexpected way during the study.

Adverse reaction: All untoward and unintended responses to an investigational medicinal product related to any dose administered.

The definition covers also medication errors and uses outside of what is foreseen in the protocol, including misuse and abuse of the product. The definition implies a reasonable possibility of a causal relationship between the event and the IMP. This means that there are facts (evidence) or arguments to suggest a causal relationship.

An Adverse Drug Reaction (ADR) is defined as all noxious and unintended responses to a medicinal product related to any dose.

An Unexpected Adverse Drug Reaction is defined as any adverse reaction, the nature of which is not consistent with the applicable product information (e.g. investigator's brochure for an unauthorized investigational product or summary of product characteristics for an authorized product).

The term ‘severity’ is used here to describe the intensity of a specific event. This has to be distinguished from the term ‘serious’.

8.2 Severity

The severity of the AE will be characterized as “mild, moderate or severe” according to the following definitions:

- Mild events are usually transient and do not interfere with the subject’s daily activities.
- Moderate events introduce a low level of inconvenience or concern to the subject and may interfere with daily activities.
- Severe events interrupt the subject’s usual daily activity.

Seriousness: The judgment as to whether the event is serious is usually made by the reporting investigator who must conform to the standard definition.

The physician will assess the seriousness, intensity, and causality of each AE, and the actions taken, including the discontinuation of the experimental drug, where required by the site investigator or the patient (Refer to GCP/1997 and to D.L N 211/2003 for explanation about how and when to refer to AE, SAE, SUSAR, DAR and their definitions).

8.3 Causality

The causal relationship between the study drug and the AE will be characterized as unrelated, unlikely, possible, probable or unknown (unable to judge). Events can be classified as “unrelated” if there is not a reasonable possibility that the study medication caused the AE.

- An “unlikely” relationship suggests that only a remote connection exists between the study drug and the reported AE. Other conditions, including chronic illness, progression, or expression of the disease state or reaction to concomitant medication, appear to explain the reported AE.
- A “possible” relationship suggests that the association of the AE with the study medication is unknown; however, the AE is not reasonably supported by other conditions.
- A “probable” relationship suggests that a reasonable temporal sequence of the AE with drug administration exists and, in the Investigator’s clinical judgment, it is likely that a causal relationship exists between the drug administration and the AE, and other conditions (concurrent illness, progression or expression of disease state or concomitant medication reactions) do not appear to explain the AE.

All efforts should be made to classify the AE according to the above categories. The category “unknown” (unable to judge) may be used only if the causality is not assessable, e.g. because of insufficient evidence, conflicting evidence, conflicting data, or poor documentation.

The assessment of whether there is a reasonable possibility of a causal relationship is made by the investigator. In the absence of information on causality from the reporting investigator, the Istituto di Ricerche Farmacologiche Mario Negri IRCCS should consult the reporting investigator and encourage him/her to express an opinion on this aspect. The causality assessment given by the investigator should not be downgraded by the Istituto di Ricerche Farmacologiche Mario Negri IRCCS. If the Istituto di Ricerche Farmacologiche Mario Negri IRCCS disagrees with the investigator's causality assessment, the opinion of both the investigator and the Istituto di Ricerche Farmacologiche Mario Negri IRCCS should be provided with the report.

For more detail about seriousness criteria, refer to "Common Terminology Criteria for Adverse Events (CTCAE)" Version 5.0 Published: Nov 27, 2017 from the U.S. DEPARTMENT OF HEALTH AND HUMAN SERVICES National Institutes of Health National Cancer Institute.

